**Practitioner). Ultimately, however, it is up to the participant to follow-up with a doctor for a clinical evaluation**

**Following the MRI, we will assess cognitive and basic motor function using the NIH toolbox the NIH Toolbox measures for Cognitive function will completed using the standard NIH Ipad (see administration manual):**

- **C.2.2 NIH Toolbox Flanker Inhibitory Control and Attention Test page 67**
- **C.2.4 NIH Toolbox Dimensional Change Card Sort Test (DCCS) page 98**
- **C.2.5 NIH Toolbox Pattern Comparison Processing Speed Test page 124**
- **C.2.7 NIH Toolbox Oral Reading Recognition Test page 151**
- **C.2.8 Oral Symbol Digit Test page 154**

**Following the NIH Toolbox measures for Cognitive function, the NIH toolbox motor measures will completed using the standard NIH Ipad (see administration manual):**

- **Pegboard dexterity test (172)**
- **Balance measures with the addition of iPod app for assessment of sway (179).**
- **Two-minute walk (198)**
- **Grip strength (using handheld dynamometer, 176)**
- **4 meter walk (195)**

**Study interaction 2 (Approximately 1 hour):** Participants will be notified via telephone which group that were randomized to.

Participants randomized to the intervention group will be sent a fitbit that has been set up to deliver the intervention as described below. We will schedule a telephone call or zoom video call (whichever the participant prefers) to set up the HIPPA compliant EMA system and to provide education about the fitbit and the intervention to disrupt sedentary time.

**Intervention (home-setting):** We will deliver content in real-time, and in the real-world environment using a wearable sensor, an activity tracker and the Illumivu mEMA smart phone app, which will enable real-time delivery of behavior options and real-time feedback on the effectiveness of behavior choices. Although the intervention will be guided by the interview findings, in general, participants will wear a Fitbit that has been programmed to deliver a notification (a buzz) when activity has ceased for more than 10 minutes. They will receive suggestions on their smartphone app on how to replace sitting time with PA such as standing up 5 times or taking 20 steps, or even performing a short (20 seconds) preferred dance routine. We will capture Fitbit data in a real-time platform (ICardia). Participants will receive reminders from their smartphones to enter

real-time feedback on activity options selected and how successful they were in adopting the option. These data will allow us to track underlying preferences for behaviors and tailor the program accordingly. Participants will receive a message immediately with positive choices for behavioral action. Resulting actions and delivery of the intervention will be automatically captured and downloaded in real time. We will teach them how to use these devices once they are assigned to the intervention group. The sensor and activity tracker will record their everyday physical activity level. When participant stays sedentary too long during a day, the smartphone app will send a real-time reminder with some physical activity options for participant to choose designed based on their preferences and focus group discussions (e.g., standing up 5 times, taking 20 steps, or performing a short dance routine). Resulting actions and delivery of the intervention will be automatically captured and downloaded into the devices in real time.

Participants randomized to the control group will be sent general guidelines for disruption of sedentary time.

Study interaction 3-Follow-up (Approximately 1 hour): At the completion of the 6-week intervention period all participants will be sent an activity monitor to be worn on the waist for 8 days to measure sedentary time: The participants will mail the monitor back to us after 8 days. Once we have received the physical activity monitor we will schedule a phone interview with the participants to understand where they had difficulty and what did or did not work for them. We will then repeat the cognitive function tests and the optional MRI scan.

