### **6.0 Study Design and Procedures**

This research will be performed via telephone/video conference to maximize social distancing and participant safety. The intervention will be performed by the participants at home.

This is a pilot randomized, controlled trial of a 6-week intervention for feasibility. Outcome measures will be obtained at baseline and at 6-weeks. Behavior choices and preference data will be continuously captured during the intervention. We will randomize 80 older Latinos from the Chicago Latino community to either an ecological momentary intervention using fitbits (n=40) or to physical activity guidelines (n=40).

Study interaction 1-baseline test (Approximately 2 hours). Participants will be screened for inclusion/exclusion criteria. If criteria for inclusion in the study are met participants will undergo informed consent process. Following informed e-consent conducted via zoom video/telephone participants will be asked about their demographics (demographic

form), and contact information (Face sheet), and then they will be asked about their medical history. Following the medical history we will fill out the Charlson co-morbidity questionnaire, and conduct the following cognitive function measures as approved by the NIH for use via video call: a. Picture vocabulary test, b. Picture sequence test, c. List sorting test, d. Oral reading recognition test, e. Auditory verbal learning test, and the Trail Making test A and B. Following the cognitive function testing, we will conduct a phone/video interview. The interview will be recorded, analyzed and used to develop the intervention.

Following the interview we will conclude the phone call and send the participants an activity monitor to be worn on the waist for 8 days to measure sedentary time: The participants will mail the monitor back to us after 8 days. Once we have received the physical activity monitor we will randomize the participant to intervention or control.

**Optional in-person visit (approximately 1 hour) If the participant is willing and able to undergo an MRI scan. No contrast will be used.**

- The MRI Visit will take place about one-week after the initial phone call. Participants will come to the Magnetic Resonance Imaging Center, 3T research center [name] and return the actigraph to us. We will ask participants to do the following:

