- **Image Analyses** DTI: FSL with TBSS, we will quantify FA and MD from whole brain and tract specific white matter. T1/FSPGR: Using FreeSurfer, we will extract hippocampal volumes (right and left) as well as sub-fields of the hippocampus adjusted for intracranial volume. T2-FLAIR: Using standard software, we will quantify white matter hyperintensity volumes across the entire brain white matter. We will use a seed-based approach to measure resting state networks of interest. *Functional connectivity networks*: Functional brain networks will be generated using the resting-state fMRI toolbox, CONN (<http://www.nitrc.org/projects/conn>; (Whitfield-Gabrieli and Nieto-Castanon, 2012)). In brief, raw EPI images are realigned, co-registered, normalized, and smoothed before analysis. Any confound effects from motion artifact, white matter, and CSF are regressed out of the signal. Using the same label maps as the structural brain networks, functional brain networks will be derived using pairwise BOLD signal correlations.

- **Feasibility and acceptability:** We will conduct formative assessments at the completion of the intervention at week 6. We will derive the number of times the phone app was accessed and the number and types of behavior choices that were made. We will review these data with participants in order to understand where they had difficulty and what did or did not work for them.

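### At follow-up the interview on what worked comes before the repeat cognitive tests, and no tester unaware of allocation is described

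*Combined protocol and SAP*

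**What the plan says.** **Follow-up order.** Section 6.0, Study interaction 3, first has an 8-day monitor wear and return by mail. After that, "we will schedule a phone interview with the participants to understand where they had difficulty and what did or did not work for them". The next sentence reads "We will then repeat the cognitive function tests and the optional MRI scan".

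**Baseline order.** Section 6.0, Study interaction 1, has the reverse: "Following the cognitive function testing, we will conduct a phone/video interview". Allocation comes later still: "Once we have received the physical activity monitor we will randomize the participant to intervention or control".

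**What each arm receives.** Section 6.0 describes the Fitbit, the app and a set-up call for the intervention group. For the other arm it says "Participants randomized to the control group will be sent general guidelines for disruption of sedentary time".

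**App-use review.** Section 8.0, under feasibility and acceptability, says "We will conduct formative assessments at the completion of the intervention at week 6". It lists app-access counts and behaviour choices, and adds "We will review these data with participants in order to understand where they had difficulty and what did or did not work for them".

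**Blinding.** Section 11.0 has two statements. Data Analysis and Coordination says the PI is not blinded to outcome data or to data that identify participants. Protection of Confidentiality says that what the Safety Officer and the monitoring committee see is blinded. Neither concerns the person giving the cognitive tests.

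**The concern.** A conversation about what helped and what was difficult will tend to bring out whether the participant had a Fitbit and app or only guidelines. Held just before the repeat tests, it can tell the tester the arm at the moment when that knowledge should be absent. At baseline the question cannot arise for the video-call tests, because they are finished before anyone is randomised.

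At stake is the exploratory aim in Section 3.0, which compares cognitive function between the randomised arms. A fatigue or order effect common to both arms would largely cancel in that comparison. Examiner expectation that depends on the arm would not, and randomisation does not remove it. The feasibility and acceptability aims, and sedentary time measured by accelerometer, do not depend on who gives the tests.

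**Working it through.** The plan states no figure on this point, so the main check sets the sections side by side.

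**1. Order of events.**

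| Stage | Sequence in Section 6.0 | Could the tester know the arm? |
|---|---|---|
| Baseline (video call) | tests, interview, monitor wear and return, randomisation | No, there is no arm yet |
| Follow-up | monitor wear and return, interview, tests | Yes, if the interview informs the tester |

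Both follow-up tasks sit under one interaction of about 1 hour. A single contact with the same staff is therefore plausible, but it is not stated.

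**2. Other routes to the same knowledge.**
- Section 6.0, Study interaction 2: "Participants will be notified via telephone which group that were randomized to". A set-up call follows for the EMI arm.
- Section 13.2: research assistants and the PI programme the messages sent to the EMI arm.
- Section 10.0: the PIs and study staff meet weekly on the data.

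None of these says that the staff concerned also give the tests, or that allocation is discussed at the meetings. They are possible routes, not established ones.

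**3. Timing of the app-use review.** Section 8.0 does not mention the repeat tests, so there are two readings.
- *Separate contact at week 6.* The intervention ends at day 6 × 7 = 42. The tests come no earlier than day 42 + 8 = 50, plus mailing time. The review then precedes testing by at least 8 days.
- *Same contact as the follow-up interview.* The purpose is worded almost identically in Sections 6.0 and 8.0, and Sections 3.0 and 6.0 use six weeks loosely for all follow-up outcomes. Moving the interview after the tests would then move the review too.

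**4. Scale, for illustration only.** The arm size of 40 comes from Section 4.0. The shift, the 20% dropout (40 × 0.8 = 32 per arm) and the baseline correlation r are assumptions; the documents give none of them. For a standardised mean difference adjusted for baseline, SE = √(2/n) × √(1 − r²).

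| n per arm | r | SE (SD units) | 0.1 SD shift, in SE | 0.2 SD shift, in SE | 1.96 × SE |
|---|---|---|---|---|---|
| 40 | 0 | 0.224 | 0.45 | 0.89 | 0.438 |
| 40 | 0.5 | 0.194 | 0.52 | 1.03 | 0.380 |
| 40 | 0.7 | 0.160 | 0.63 | 1.25 | 0.313 |
| 32 | 0 | 0.250 | 0.40 | 0.80 | 0.490 |
| 32 | 0.5 | 0.217 | 0.46 | 0.92 | 0.424 |
| 32 | 0.7 | 0.179 | 0.56 | 1.12 | 0.350 |

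A shift of 0.2 SD would be close to one standard error in size, yet inside the 95% half-width in every row. The table shows only that a bias of that size could not be told from chance using the scores. It is not evidence that such a bias exists.

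**The case against.** **The tester may not be the interviewer, and staff may know the arm anyway.** The documents do not say who interviews or who tests. If the two are different people, the interview need not inform the tester; if the tester already knows the arm by another route, reordering achieves little. Both points stand. They are why disclosure is called likely only on the condition that the same staff do both, and why an awareness record is needed besides the reordering.

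**This is a feasibility pilot, so interview-first is defensible.** Aim 3 is feasibility and acceptability; cognition is exploratory and its analysis mainly descriptive. Section 7.0 grants that participants may find the testing boring or tiring, so an interview held afterwards may yield thinner answers. The point stands as a cost. It is small where the interview simply moves behind the tests at the same follow-up stage. It is larger if the app-use review was meant as a separate week-6 contact.

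**The tests are standardised.** Section 6.0 cites NIH-approved measures for video calls, and an administration manual for the in-person battery. This limits examiner influence without removing it.

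**The numbers are assumed.** They are, and the point does not rest on them.

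**Conclusion.** The point holds as a modest, inexpensive improvement. The plan reverses its own protective baseline order at follow-up without giving a reason, and describes no cognitive tester unaware of allocation. If the same staff interview and test, the arm is likely to be known before testing. The exploratory cognitive comparison could then be biased by an unknown amount in an unknown direction.

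A reader might infer more than the documents support:
- *That the app-use review is fixed before the tests.* Section 8.0 never mentions the tests and may describe the same contact as the interview.
- *That the PI is declared unblinded to allocation.* Section 11.0 refers to outcome and identifying data, and offers the small, brief, single-site design as its reason.
- *That testers will be unblinded, or that the bias favours EMI.* Testers and interviewers are not identified. The interview guide and telephone script are listed as appendices but were not available to check.
- *That the pilot as a whole is compromised.* Feasibility, acceptability and accelerometer-measured sedentary time are untouched.

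**What to change.** 1. Reword the end of Section 6.0, Study interaction 3, so that once the monitor is back the video-call cognitive tests are repeated first and the interview follows straight after.
2. State in Section 8.0 that app-use data are reviewed with participants at that same post-test interview. This settles the timing on either reading.
3. Ask participants not to mention their group until testing ends.
4. For each follow-up cognitive test, by video call or in person, record whether the tester knew the allocation, and report this by arm. This matters most for any in-person tests repeated around the optional MRI, which may fall after the interview.
5. Where existing staffing allows, have the tests given by a team member not involved in the allocation call, device set-up or messaging.

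**Cost.** Two wording changes, one instruction to participants and one form field, with no added tests and no extra staff required. The interview follows testing, with some possible fatigue. If the app-use review was intended as a separate week-6 contact, it moves later by at least 8 days plus return mail for EMI participants, with some added recall time. The reordering lowers the chance of disclosure without ensuring blinding; the awareness record shows how far the risk remained.

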## **7.0 Expected Risks/Benefits**

### **Risk associated with the medical history assessment**

Discomfort could be felt by participants when answering questions about their medical history.

### **Risk associated with the cognitive function questionnaires.**

There is a slight risk that participants will feel uncomfortable with filling out the questionnaires. Participants could find answering the questions boring and/or tiring. We will monitor the progress and allow participants to take breaks as needed. If they become upset or uncomfortable, they may skip a given question.

### **Optional MRI scans:**

The MRI scans are performed with a powerful magnet without using x-ray radiation or radioactive material. The magnetism of the machine attracts certain metals, which could put a participant at risk. Therefore, people with pacemakers, infusion pumps, metal

prostheses, metallic-backed transdermal patches or metallic shrapnel will be excluded from the study. A checklist will be completed that addresses issues of MRI safety. Some people may feel somewhat closed-in (claustrophobic) during the MRI procedure. The MRI scans can get quite noisy and this may cause some discomfort. We will provide padding, a blanket as well as ear plugs to ensure comfort. Participants will stay in contact with study staff during the entire MRI procedure and can request to stop at any time.

#### **Risk associated with the intervention.**

There are no known risks associated with activities to break up sedentary time as they are considered usual activities of daily living.

### **8.0 Data Collection and Management Procedures**

- We will use EMI designed to deliver content in real-time, and in the real-world environment. EMI, using a wearable sensor, an activity tracker and the Illumivu mEMA smart phone app, will enable real-time delivery of behavior options and real-time feedback on the effectiveness of behavior choices. This methodology will enable us to create a culturally appropriate intervention that is based on preferences of individuals within their community networks. Although the intervention will be guided by the focus group findings, in general, we expect that participants will wear a Fitbit that has been programmed to deliver a notification (a buzz) when activity has ceased for more than 10 minutes. They will receive a notification on their smartphone app with a suggestion on how to replace sitting time with PA such as standing up 5 times or taking 20 steps, or even performing a short preferred dance routine. We will capture Fitbit data in a real-time platform (ICardia). Participants will receive reminders from their smartphones to enter real-time feedback on the PA options selected and how successful they were in adopting the option. These data will allow us to track underlying preferences for behaviors and tailor the program accordingly. Participants will receive a message immediately with positive choices for behavioral action. Resulting actions and delivery of the intervention will be automatically captured and downloaded in real time.
- **Outcomes: Sedentary time** will be measured using the Actigraph, a validated tool for measuring sedentary time in older adults following standard procedures over 7 days at baseline and at follow up. Sedentary behavior will be defined as: 1) waking activity with an energy expenditure  $\leq 1.5$  metabolic equivalents occurring in a sitting or reclining posture; 2) vector magnitude counts are  $<70$  counts/15-s and vertical axis counts are  $<10$  counts/15-s. Sedentary interruption will be defined as counts  $>100$ /minute. Non-wear time will be considered to be 60 minutes of zero-activity counts. Any counts over 15,000 will be considered erroneous. A valid day will consist of 10 waking hours. At least 5 complete days of data must be available to be included in the analysis.
- **Cognitive and Physical Function Measures** will be assessed using the NIH Toolbox measures.

- **Image acquisition** will be performed on GE 3T MRI research dedicated scanner (MR 750) pre- and post-intervention. After a brief scout image for localization, we will acquire whole brain images using diffusion tensor imaging (DTI); and high-resolution 3D T1-weighted imaging. We will determine and quantify white matter integrity (DTI-FA/MD); and hippocampal volume (T1). These are indices of alterations of brain interconnections, structure, and function, which are associated with cognitive functioning (details, table 2).

Table 2. Imaging Parameters

Technique	Purpose	Parameters (TE=echo time; TR=repetition time; BW=bandwidth; FOV=field of view; TI=inversion time)
DTI	White matter integrity (FA/MD) quantification	single-shot EPI & parallel imaging using the same 32-channel phased-array head coil; TE/TR~70/5525ms, b-values 0,1000s/mm  , 33 directions, FOV=20cm  , matrix 160x160, NEX 2, parallel imaging acceleration factor 2; 6 B0 images, Slice thickness 3 mm
T1/BRAVO	Hippocampal Volume Quantification	Coronal; TI=4.5, Flip=13°, 1.5mm slice thickness, no gap, BW=±25kHz, FOV=22cm 
T2-FLAIR	White matter hyperintensity quantification	Coronal; TE/TR=104.5/9500ms, TI=2.5sec, FOV 22cm 
ASL	Cerebrovascular perfusion Cerebral blood flow	axial; Spiral-FSE acquisition; post-label delay time = 1.8 sec, TE/TR=minimum, flip angle=90°, slice thickness = 3-5 mm, matrix size = 128x128, FOV 22cm 
Resting-state fMRI	Resting state networks	Subjects will be instructed to keep their eyes open, focus on a fixation point, and “not think of anything in particular”. Resting-state data will be acquired: total scan time = 8 minutes.

- **Image Analyses** DTI: FSL with TBSS, we will quantify FA and MD from whole brain and tract specific white matter. T1/FSPGR: Using FreeSurfer, we will extract hippocampal volumes (right and left) as well as sub-fields of the hippocampus adjusted for intracranial volume. T2-FLAIR: Using standard software, we will quantify white matter hyperintensity volumes across the entire brain white matter. We will use a seed-based approach to measure resting state networks of interest. *Functional connectivity networks*: Functional brain networks will be generated using the resting-state fMRI toolbox, CONN (<http://www.nitrc.org/projects/conn>; (Whitfield-Gabrieli and Nieto-Castanon, 2012)). In brief, raw EPI images are realigned, co-registered, normalized, and smoothed before analysis. Any confound effects from motion artifact, white matter, and CSF are regressed out of the signal. Using the same label maps as the structural brain networks, functional brain networks will be derived using pairwise BOLD signal correlations.

- **Feasibility and acceptability:** We will conduct formative assessments at the completion of the intervention at week 6. We will derive the number of times the phone app was accessed and the number and types of behavior choices that were made. We will review these data with participants in order to understand where they had difficulty and what did or did not work for them.

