## 9.0 Data Analysis

- We will conduct a thematic analysis to explore themes from individual phone interviews. Feasibility and acceptability will be assessed using descriptive and non-parametric statistics. Exploratory analyses will be conducted to assess for trends and effect sizes. [name] of the College of Nursing statistician will conduct all analyses. The apriori stated analysis is listed below.  
This is a pilot study for feasibility. For these pilot data we will emphasize descriptive statistics such as means, standard deviations, effect sizes, medians, interquartile ranges, frequencies, and percentages to demonstrate the feasibility of recruitment, adherence, and retention, treatment effects over time, and proof of concept. Our statistical approach for a full trial of these hypotheses will be Generalized Linear Mixed Models (GLMM) with an identity link function for a continuous outcome or a logit link function for a binary outcome. Conceptually, GLMM is a more advanced version of repeated measures ANOVA that can account for potential correlation among multiple measurements over time while having flexibility in fitting outcomes with different distributions (such as normal, binomial or Poisson, etc.). One advantage of this approach over repeated measures ANOVA is that there is no assumption that participants are measured at every, or even the same, time points. Therefore, these models are very flexible at handling missing data. Participants who have a missing observation are not excluded, thus, this produces the intention to treat (ITT) full information maximum likelihood (FIML) model. Conducting these models on pilot data help with sample size calculations for a future R01 submission.

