- Internet-based application/package –Specify: iCardia: Remote collection of Fitbit data and delivery of text-messages will be done via iCardia, a secure, password-protected, internet-based application that has been developed at UIC and is currently hosted in a HIPAA-compliant server at the ACCC Secure Research Environment. Text-messages will be programmed in the iCardia system by the RAs and the PI, based on each person's responses to the interview at baseline and will be sent to study participants based on their preferences captured at baseline. Participants will be able to change their preferred days/hours by responding to the text-messages sent. Participants who no longer wish to receive reminders or text-messages may reply with "STOP." iCardia automatically will stop sending messages if this is received; thus, messages will be immediately discontinued without requiring contact with research

team. iCardia is password protected and will only be accessed by the PI and key research personnel at UIC through an encrypted, Secure Sockets Layer/VPN connection. iCardia will be used in this study for two purposes: (1) to send motivational text-messages about breaking up sedentary time to study participants in the intervention group; and (2) to remotely collect Fitbit data pertaining to participants' physical activity (steps, minutes of activity, intensity of activity, sedentary minutes, etc.). Storing and exportation of Fitbit data from iCardia is done using Subject ID codes only. Text-messages send from iCardia will not contain patient health information or any other sensitive data.

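### App engagement in the EMI arm is planned as raw counts with no prompt denominator, so the counts mix how many prompts a person received with how often they responded

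*Combined protocol and SAP*

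**What the plan says.** Under the feasibility and acceptability item of section 8.0, the measures of app use are counts: "We will derive the number of times the phone app was accessed and the number and types of behavior choices that were made". They are to be reviewed with participants at week 6 to learn what worked. No denominator is given, whether prompts delivered, wear time or sedentary bouts.

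Sections 9.0 and 12.0 (same text) say descriptive statistics will be used "to demonstrate the feasibility of recruitment, adherence, and retention, treatment effects over time, and proof of concept". Neither section defines adherence.

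The prompts follow behaviour. The Fitbit is "programmed to deliver a notification (a buzz) when activity has ceased for more than 10 minutes" (sections 6.0 and 8.0). For the app's activity options, section 6.0 says: "When participant stays sedentary too long during a day, the smartphone app will send a real-time reminder with some physical activity options". Neither section says whether an ignored prompt is repeated while the person stays seated.

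Not every message is tied to inactivity. Participants are also reminded to enter feedback in the app (sections 6.0 and 8.0). Section 13.2 describes iCardia texts sent by preference: "Participants will be able to change their preferred days/hours by responding to the text-messages sent".

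Delivery is logged: "Resulting actions and delivery of the intervention will be automatically captured and downloaded in real time" (sections 6.0 and 8.0). A denominator could therefore be built, but none is specified.

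**The concern.** A count of choices is, in large part, the number of prompts received multiplied by the proportion answered. The first factor depends on sitting, which is the behaviour the intervention is meant to change. The second is what a reader would take engagement to mean. Reported without a denominator, the count cannot separate them.

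Two readings are at risk. Across people, someone who still sits a great deal can log more choices than someone who responds better but is prompted less. Over time, a decline across the six weeks could mean that people stopped responding, stopped wearing the tracker, or started interrupting sitting on their own.

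Aim 3 is the feasibility and acceptability of the EMI, and sections 9.0 and 12.0 say the pilot will inform a larger application. How engagement is described is therefore one of the main things the pilot delivers.

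**Working it through.** **Inputs from the document.** The buzz fires after more than 10 minutes without activity (sections 6.0 and 8.0). The intervention lasts 6 weeks, so 6 × 7 = 42 days (section 6.0). The EMI arm has 40 people, and only they use the app. The plan gives no prompt rate, response rate, adherence figure or re-prompt rule, so there is no planned figure to reproduce. **Every prompt rate, response rate, sitting time and bout length below is an assumption for illustration.**

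**Formulas.** Choices = prompts per day × proportion answered × 42. Response proportion = choices ÷ prompts delivered.

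**Step 1: same response, different exposure.** At 50% answered:
- 30 prompts/day: 30 × 0.5 × 42 = 630 choices out of 1,260 prompts, or 50%.
- 15 prompts/day: 15 × 0.5 × 42 = 315 choices out of 630 prompts, or 50%.

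The count halves while the response proportion is unchanged. The two-fold gap is simply the assumed two-fold gap in prompts. At the limit, someone never inactive for more than 10 minutes receives no buzz.

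**Step 2: can ranks change?** Compare person A, still sedentary, with person B, who interrupts sitting unprompted.

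| Person | Prompts/day | Answered | Prompts, 42 days | Choices, 42 days |
|---|---|---|---|---|
| A | 30 | 50% | 1,260 | 630 |
| B | 10 | 90% | 420 | 378 |
| B | 15 | 90% | 630 | 567 |
| B | 20 | 90% | 840 | 756 |

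B ranks below A on the count when B's prompts are fewer than 30 × 0.5/0.9 = 16.7 a day, which is 56% of A's. Above that, the count and the proportion agree on the order.

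**Step 3: the re-prompt rule.** Assume 8 h of sitting a day in 60-minute bouts, with possible prompts at 10, 20, 30, 40 and 50 minutes, and ignore the time the action takes. There are 8 × 42 = 336 bouts.
- *Ignored prompts repeat.* Everyone gets 5 × 336 = 1,680 prompts. Choices are 0.1 × 1,680 = 168 at 10% response and 0.9 × 1,680 = 1,512 at 90%. The counts differ nine-fold, as the response rates do.
- *Ignored prompts do not repeat within a bout.* Expected prompts per bout are 1 + r + r² + r³ + r⁴, where r is the proportion answered. At r = 0.1 this is 1.1111, giving 373 prompts and 37 choices. At r = 0.9 it is 4.0951, giving 1,376 prompts and 1,238 choices. A nine-fold difference in response becomes about 33-fold in counts (1,238/37.3).

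Under the second rule, at fixed sitting time, the better responder receives more prompts, and the count exaggerates the difference instead of hiding it.

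**Step 4: less sitting.** For the 90% responder, going from 8 to 4 to 2 bouts a day gives 1,512, 756 and 378 choices with repeats, and 1,238, 619 and 310 without. Under either rule the count falls in proportion to sitting while response stays at 90%.

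**The case against.** A reader might infer more: that the plan measures adherence by these counts, that people who succeed will look less adherent, and that the adherence conclusion could be reversed. The documents do not support that reading.

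- Section 8.0 presents the counts as formative feasibility and acceptability information. Adherence is undefined, not defined wrongly, and the statistics listed in sections 9.0 and 12.0 include percentages.
- The counts are not the only feasibility measures. Recruitment and retention are named in sections 9.0 and 12.0, and a participant satisfaction survey is listed among the appendices.
- The iCardia texts follow preferred days and hours, and nothing says the app can be opened only after an inactivity prompt.
- The direction is not fixed. Someone who answers each prompt and sits down again can receive more prompts than someone who ignores them (step 3).
- How prompts behave when the Fitbit is off is not stated, and a fall caused by non-wear is partly real non-adherence.
- No threshold, progression rule or test uses the counts.
- Delivery is logged, so a ratio could be computed later.

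All of these points stand, and they narrow the concern. They do not make the raw count interpretable by itself. It is still the only named app-engagement measure, and it still combines exposure with response whichever re-prompt rule applies. Choosing the ratio in advance is also better than choosing it after the logs have been seen.

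**Conclusion.** The point holds in a limited form. The named app-engagement measures for the 40 people in the EMI arm are counts without a denominator, and adherence is promised but not defined. Since the buzz and the app options depend on inactivity, a low or falling count cannot be assigned to disengagement, non-wear or success.

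No single size can be given. The count moves in proportion to prompts received at a given response, but actual prompt rates, response rates and the re-prompt rule are unknown. The figures above show the mechanism and do not predict results. The rank change in step 2 needs a large gap in prompts and is a possibility only.

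The effect is confined to how engagement in the EMI arm is described. The comparison between randomised groups and sedentary time, which the Actigraph measures separately, are untouched. This is a worthwhile, inexpensive improvement and does not threaten the trial's validity.

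**What to change.** In the feasibility and acceptability item of section 8.0, and in sections 9.0 and 12.0:

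1. Define app engagement (adherence to prompts) as the proportion of delivered inactivity-triggered app prompts answered with a recorded choice, on days with Fitbit wear, summarised per person and by week.
2. Say what counts as a delivered prompt, keeping the app notification distinct from the Fitbit buzz, and how a choice is matched to a prompt.
3. Report prompts delivered per wear-hour, and wear time, beside the proportion. The first describes behaviour, the second device use. Show person-weeks with no prompts separately, because the proportion is undefined there.
4. Count scheduled iCardia texts separately.
5. Document the re-prompt rule as implemented.
6. Keep the raw counts of accesses and choices as supporting description.

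The cost is analysis wording, a Fitbit wear-day definition (the valid-day rule in section 8.0 is for the Actigraph), and a merge of the app log with the iCardia data through the participant codes the investigators hold. No new data collection is indicated, provided the log keeps one record per delivered prompt. The team should confirm that.
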